If ANOVA indicates a significant overall difference, pairwise t-tests will test the following hypotheses:

Hypothesis 14a. There will be no statistically significant 12 month follow up minus post-treatment mean differences across the four treatment groups in self report of extent of satisfaction or dissatisfaction with ability to get to sleep at bedtime;

Hypothesis 14b. There will be no statistically significant 12 month follow up minus post-treatment mean differences across the four treatment groups in self report of extent of satisfaction or dissatisfaction with frequency of awakenings after having initiated sleep;

Hypothesis 14c. There will be no statistically significant 12 month follow up minus post-treatment mean differences across the four treatment groups in self report of extent of satisfaction or dissatisfaction with ability to return to sleep after awakenings during the night;

Hypothesis 14d. There will be no statistically significant 12 month follow up minus post-treatment mean differences across the four treatment groups in self report of extent of satisfaction or dissatisfaction with average quantity of sleep;

Hypothesis 14e. There will be no statistically significant 12 month follow up minus post-treatment mean differences across the four treatment groups in self report of extent of satisfaction or dissatisfaction with overall quality of sleep.

Hypothesis 15: Satisfaction with Treatment

There will be no statistically significant differences across treatment types in post-treatment reported overall level of satisfaction with the treatment received as measured with a 5-point Likert Scale on the FEEDBACK QUESTIONNAIRE.

Hypothesis 16: Likelihood to Recommend to Others

There will be no statistically significant differences across treatment types in post-treatment reported level of likelihood to recommend to others the treatment received as measured with a 5-point Likert Scale on the FEEDBACK QUESTIONNAIRE.

MISSING DATA

All data measures will be reviewed upon receipt to ensure no data is missing. Subjects who have not completed the data measures and/or specific items will be asked to do so immediately upon the review having identified missing data. In any situations in which important missing data cannot be gathered, the subject will be eliminated from the study. It is anticipated that in effect 5-10% of subjects will not

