The Research Coordinator will direct the participant to arrive a few minutes early and to check in at the front desk in the first floor reception area. The participant will be told to tell the receptionist their name, the name of their treatment provider, and that they are receiving treatment for insomnia in the Insomnia Clinical Research Trial.

The Research Coordinator will schedule the participant with one of the treatment providers. The treatment will be at either 11:00am, 12 noon or 2:00pm depending on which one hour block of time that treatment provider has reserved for treatment delivery. The Research Coordinator will schedule the initial session in Practice Fusion with 5 weekly repeats. The Research Coordinator will then send an email to the treatment provider indicating the name of the client, the time and date on which the first session is scheduled, and the treatment the provider is to deliver (FOA, CBT-I, Combined and Sleep Hygiene).

CLINICAL PROCEDURES

The study staff will follow the six session protocol for treatment delivery. Each of the six sessions is scripted so as to provide standardization, and the study staff will generally be reading the script. The first session is identical across all four treatments. For specifics, see file folders entitled CBT-I, FOA, Combo and Sleep Hygiene.

DATA GATHERING DURING TREATMENT

Ongoing self-report data pertaining to the participant's sleep using a Weekly Sleep Log. Weekly Sleep Logs will be completed by the participant and brought to each treatment session. At the beginning of each session, the study staff will review the Weekly Sleep Log for completion. After the treatment session has ended and during the same day, the study staff will forward the Weekly Sleep Log to the Research Coordinator.

The Research Coordinator will enter the following information onto the DATA SHEET:

1. SL; Sleep Latency (time to fall asleep in minutes)
2. NOA: Number of Awakenings
3. WASO: Wake After Sleep Onset (in minutes)
4. SL + WASO (in minutes)
5. TOB: Total Time Out of Bed in minutes
6. TST: Total Sleep Time (in minutes)
7. TIB: Time In Bed (total, in minutes)
8. SE: Sleep Efficiency = TST/TIB (as a decimal)

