9.1.3 SAFETY FOLLOW UP PERIOD

Coordinated and administered by Research Coordinator. Completed after last treatment session; can be on that day but not before the treatment session; must be no later than one week after that date.

FEEDBACK QUESTIONNAIRE:

1. Beck Depression Inventory (BDI)
2. Beck Anxiety Inventory (BAI)
3. Insomnia Severity Index (ISI)
4. Self-Report Sleep Measures (SRSM)
5. Clinical Global Impression (CGI)
6. Clinical Global Impression – Severity scale (CGI-S)
7. Quality of Life Enjoyment and Satisfaction (Q-LES)
8. Columbia Suicide Severity Rating Scale (C-SSRS)

THREE MONTH FOLLOW UP:

WEEKLY SLEEP LOG (WSL)

Data entry completed for one week at each administration [At in person intake, each week during treatment and at 3, 6 and 12 months]

[Each of the following is needed for data entry as an average for the last 7 nights]

1. SL; Sleep Latency (time to fall asleep in minutes)
2. NOA: Number of Awakenings
3. WASO: Wake After Sleep Onset (in minutes)
4. SL + WASO (in minutes)
5. TOB: Total Time Out of Bed in minutes
6. WASO: Waking Time After Sleep Onset in minutes
7. TST: Total Sleep Time (in minutes)

8. **TIB: Time In Bed (total, in minutes)**
9. **SE: Sleep Efficiency = TST/TIB (as a percentage)**
10. **Beck Depression Inventory (BDI)**
11. **Beck Anxiety Inventory (BAI)**
12. **Insomnia Severity Index (ISI)**
13. **Self-Report Sleep Measures (SRSM)**
14. **Clinical Global Impression (CGI)**
15. **Clinical Global Impression – Severity scale (CGI-S)**
16. **Columbia Suicide Severity Rating Scale (C-SSRS)**

SIX MONTH FOLLOW UP:

This is the same as the THREE MONTH FOLLOW UP except that the following three are added.

1. **Beck Depression Inventory (BDI)**
2. **Beck Anxiety Inventory (BAI)**
3. **Insomnia Severity Index (ISI)**
4. **Self-Report Sleep Measures (SRSM)**
5. **Clinical Global Impression (CGI)**
6. **Clinical Global Impression – Severity scale (CGI-S)**
7. **Columbia Suicide Severity Rating Scale (C-SSRS)**

TWELVE MONTH FOLLOW UP:

[figure not shown]
This is the same as the SIX MONTH FOLLOW UP adding the Feedback Questionnaire.

1. **Beck Depression Inventory (BDI)**
2. **Beck Anxiety Inventory (BAI)**
3. **Insomnia Severity Index (ISI)**
4. **Self-Report Sleep Measures (SRSM)**
5. **Clinical Global Impression (CGI)**
6. **Clinical Global Impression – Severity scale (CGI-S)**
7. **Columbia Suicide Severity Rating Scale (C-SSRS)**

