9.4.2 METHOD OF ASSIGNING PATIENTS TO TREATMENT GROUPS

The Research Coordinator will determine the scheduling:

If you participate, your time commitment will include six one hour appointments with your study staff. These appointments will be on a weekday day, at 11:00am, 12:00 noon or 2:00pm. As a participant, you will be assigned to on weekday for a one hour appointment for six consecutive weeks. Please put an X beside each time that works for you on each day.

Monday@		11:00am;		12:00 noon;		2:00pm
Tuesday@		11:00am;		12:00 noon;		2:00pm
Wednesday@		11:00am;		12:00 noon;		2:00pm
Thursday@		11:00am;		12:00 noon;		2:00pm

Treatment providers will be required to declare at least one and preferably two of these times (11am, noon and/or 2pm) as times they will be available to delivery treatment, given two week notice of a participant being assigned. The Research Coordinator will make effort to inform each provider when it is likely they will be assigned a new participant.

The Research Coordinator will inform the treatment provider one week in advance of a probably participant being assigned, also informing the treatment provider of the treatment to be utilized (FOA, CBT-I, Combined and Sleep Hygiene).

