9.4.5 END OF TREATMENT

SAFETY FOLLOW UP PERIOD

Coordinated and administered by Research Coordinator. Completed after last treatment session; can be on that day but not before the treatment session; must be no later than one week after that date.

FEEDBACK QUESTIONNAIRE:

1. Beck Depression Inventory (BDI)
2. Beck Anxiety Inventory (BAI)
3. Insomnia Severity Index (ISI)
4. Self Report Sleep Measures (SRSM)
5. Clinical Global Impression (CGI)
6. Clinical Global Impression – Severity scale (CGI-S)
7. Quality of Life Enjoyment and Satisfaction (Q-LES)
8. Columbia Suicide Severity Rating Scale (C-SSRS)

THREE MONTH FOLLOW UP:

WEEKLY SLEEP LOG (WSL)

Data entry completed for one week at each administration [At in person intake, each week during treatment and at 3, 6 and 12 months]

[Each of the following is needed for data entry as an average for the last 7 nights]

1. SL; Sleep Latency (time to fall asleep in minutes)
2. NOA: Number of Awakenings
3. WASO: Wake After Sleep Onset (in minutes)
4. SL + WASO (in minutes)

5. **TOB: Total Time Out of Bed in minutes**
6. **WASO: Waking Time After Sleep Onset in minutes**
7. **TST: Total Sleep Time (in minutes)**
8. **TIB: Time In Bed (total, in minutes)**
9. **SE: Sleep Efficiency = TST/TIB (as a percentage)**
10. **Beck Depression Inventory (BDI)**
11. **Beck Anxiety Inventory (BAI)**
12. **Insomnia Severity Index (ISI)**
13. **Self Report Sleep Measures (SRSM)**
14. **Clinical Global Impression (CGI)**
15. **Clinical Global Impression – Severity scale (CGI-S)**
16. **Columbia Suicide Severity Rating Scale (C-SSRS)**

SIX MONTH FOLLOW UP:

This is the same as the THREE MONTH FOLLOW UP except that the following three are added.

1. **Beck Depression Inventory (BDI)**
2. **Beck Anxiety Inventory (BAI)**
3. **Insomnia Severity Index (ISI)**
4. **Self Report Sleep Measures (SRSM)**
5. **Clinical Global Impression (CGI)**
6. **Clinical Global Impression – Severity scale (CGI-S)**
7. **Columbia Suicide Severity Rating Scale (C-SSRS)**

TWELVE MONTH FOLLOW UP:

This is the same as the SIX MONTH FOLLOW UP adding the Feedback Questionnaire.

1. **Beck Depression Inventory (BDI)**
2. **Beck Anxiety Inventory (BAI)**
3. **Insomnia Severity Index (ISI)**
4. **Self Report Sleep Measures (SRSM)**
5. **Clinical Global Impression (CGI)**
6. **Clinical Global Impression – Severity scale (CGI-S)**
7. **Columbia Suicide Severity Rating Scale (C-SSRS)**

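### The immediate-completion rule for missing items does not exempt the Weekly Sleep Log, so blank nights can be filled from recall, unmarked, in front of staff who know the arm

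*Protocol*

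**What the plan says.** Protocol Section 8.0, Missing Data, sets one rule for every instrument. The review is universal: "All data measures will be reviewed upon receipt to ensure no data is missing". The remedy for a gap is that "Subjects who have not completed the data measures and/or specific items will be asked to do so immediately". The fallback is that "In any situations in which important missing data cannot be gathered, the subject will be eliminated from the study". Important is not defined, and no instrument is exempted.

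Sections 9.1.2 and 9.4.4 (Data Gathering During Treatment) describe the sleep log: "Weekly Sleep Logs will be completed by the participant and brought to each treatment session", and then "At the beginning of each session, the study staff will review the Weekly Sleep Log for completion". The log goes to the Research Coordinator the same day. Sections 9.1.3 and 9.4.5 say of the log variables: "Each of the following is needed for data entry as an average for the last 7 nights".

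The trial is open label. Section 9.4.2 has the Research Coordinator notify the provider ahead of time, "also informing the treatment provider of the treatment to be utilized (FOA, CBT-I, Combined and Sleep Hygiene". The assessment after the last session is "Coordinated and administered by Research Coordinator", and the coordinator also keeps the assignment spreadsheet. Hypotheses 1 and 8 in Section 8.0 use sleep latency, wake after sleep onset, total sleep time and sleep efficiency from the log, as change from pre-treatment to post-treatment and to 12 months.

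**The concern.** Asking someone to answer a skipped item on a form just handed in costs nothing in validity, because the recall period of the form is unchanged. A log covering the past seven nights is different. An entry missing for a night five days ago cannot be collected now as it would have been the next morning. It can only be reconstructed.

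In an open-label comparison of behavioural treatments, reconstructed values can absorb what the participant expects of the treatment or wants the staff member to see. Once written in without a mark, they look like any other entry, so no later analysis can remove them. The protocol's own missing-data check, a t-test on Insomnia Severity Index totals between subjects with and without missing data, would not detect the problem, because a log filled in this way counts as complete. A visible missing-data problem could therefore become a hidden measurement problem in the sleep-log outcomes.

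**Working it through.** The protocol states no figure for this point, so there is nothing to reproduce. The check is mainly one of reading the sections together.

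**Does the rule reach the log?** Yes, by its scope. Section 8.0 covers all measures and specific items, and nothing in Sections 9.1.2, 9.1.3, 9.4.4 or 9.4.5 takes the log out. Those sections give no minimum number of nights for a weekly average, no entry date and no flag for late entries.

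**Who is present?**
- Treatment-week logs: the staff delivering the treatment, at the start of the session.
- End-of-treatment and follow-up logs: the Research Coordinator, outside the treatment session.
- Both know the arm.

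**Which logs enter the analysis?** The visit lists in Section 9.5.3 place a log at Visit 1 (screening), Visit 8 (one week after treatment) and Visit 11 (12 months). Hypothesis 1 contrasts pre- and post-treatment; Hypothesis 8 contrasts pre-treatment and 12 months. Mid-treatment logs enter neither contrast. Section 9.5.3.2 puts randomisation at Visit 2, so recall in the Visit 1 log should add noise rather than arm-dependent error. The differential risk sits mainly in the Visit 8 and Visit 11 logs.

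**Size for one participant.** Shift in the seven-night mean = k × m / 7, with k nights filled and m minutes of recall bias per night (both assumed).
- 1 night, 10 minutes: 1 × 10 / 7 = 1.4 minutes
- 2 nights, 20 minutes: 2 × 20 / 7 = 5.7 minutes
- 3 nights, 30 minutes: 3 × 30 / 7 = 12.9 minutes

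**Size for an arm comparison.** Shift = s × k / 7 × d, where s is the share of participants affected and d is the between-arm difference in recall bias. With s = 0.30 (assumed):
- k = 1, d = 10: 0.30 × 1.43 = 0.4 minutes
- k = 2, d = 20: 0.30 × 5.71 = 1.7 minutes
- k = 3, d = 30: 0.30 × 12.86 = 3.9 minutes

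**How common might blank nights be?** With an assumed miss rate p per night, independent between nights, the chance that a seven-night log has at least one blank is 1 − (1 − p)^7:

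| p | At least one blank night in 7 |
|---|---|
| 1% | 6.8% |
| 2% | 13.2% |
| 5% | 30.2% |
| 10% | 52.2% |

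The 30% share is thus the share with any blank night at p = 5%. Giving each of those logs two filled nights means 0.30 × 2 / 7 = 8.6% of all nights are filled, which is more than 5%. The 1.7-minute example is therefore on the high side for that miss rate.

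**The case against.** The strongest reply is that the rule has been assembled from separate sections. The Missing Data paragraph mentions neither the log nor the session. The data-gathering sections tell staff to review the log and pass it on, not to have past nights filled in, and receipt could mean receipt by the coordinator. The log form is not among the appendices, so it may carry instructions or entry dates that cannot be seen here. A seven-night window does not forbid averaging the nights recorded. The improvement measure named in the objectives, the Self Report Sleep Measures, is itself a recall questionnaire, and same-morning entries in an open-label trial also carry expectation.

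Much of this limits the claim. A reader might infer that participants must invent nights in session under threat of removal. The text does not support that. It says asked; recall is not invention; elimination is tied to undefined important data; and the scheduling script read to participants mentions discontinuation only for missed sessions. Nor does every log filled in before a provider feed Hypotheses 1 and 8, as the visit lists show. A reader might also set 5.7 or 12.9 minutes against the 30 to 45 minute improvement in sleep latency cited for CBT-I in the Introduction. That compares one participant's shift with a reported improvement that is not a contrast with sleep hygiene, so it does not measure bias in this trial.

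What stands is that an all-measures instruction to complete at once, with elimination behind it, has no exception for the one instrument where completing at once means recalling past nights. That is a data-collection rule, and an analysis plan cannot undo it once the entries are unmarked.

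**Conclusion.** The point holds as a defect in a stated data-collection rule. As written, blank log nights would be reconstructed from recall up to a week later in front of staff who know the arm, and the protocol does not provide for marking them. In the post-treatment or 12-month log this is possible differential measurement error in Hypotheses 1 and 8; in the pre-treatment log it is error that should not depend on arm.

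The size is unknown. The share affected, the nights filled and the between-arm difference in recall bias are all assumptions. Over the ranges shown the arm-level shift runs from 0.4 to 3.9 minutes, with 1.7 minutes as the worked example. No figure in the protocol shows that such a bias would occur. The change should be made, and before data collection, because late entries cannot be identified afterwards; but the log is not the measure named for insomnia improvement, and the point does not by itself undermine the trial.

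**What to change.** Amend the Missing Data paragraph of Section 8.0 and cross-refer to it from Sections 9.1.2, 9.1.3, 9.4.4 and 9.4.5:

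- Limit immediate completion to questionnaires filled in on site that day.
- For the Weekly Sleep Log, leave missed nights blank, or record the date of each entry and flag any made after the morning concerned.
- Average the recorded nights, with a fixed minimum (for example 4 of 7) applied equally in all arms.
- Keep flagged entries out of the main analysis and include them in a sensitivity analysis.
- Do not eliminate a participant for missing nights.

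The cost is one paragraph and a date-entered column on the log. Some weekly means will rest on fewer nights and be slightly less precise. Questionnaires lose nothing, since Section 9.1.2 already has staff check them for completeness when they are handed in at screening.

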complete 12 month follow-up. These subjects will then be eliminated as relates to analyses involving 12 month follow-up data. Statistical analyses will be conducted to determine whether those with missing data differ significantly from those without missing data using t test comparing the two groups on total scores on Insomnia Severity Index at pre-treatment as well as post-treatment.

STATISTICS

Repeated measures analysis of variance (2 X 4 ANOVA) will be used to test the Hypotheses 1-3, 5-10 and 11-16. Any statistically significant ANOVAs will be followed by pairwise t-test comparisons to identify between group differences. Chi square will be used to test Hypotheses 4 and 11.

SAFETY ANALYSIS

In general the potential risks for participants are minimal. The treatment approaches involved in related studies have been shown to be a safe procedure and in most of the published studies people who underwent these procedures did not report any harmful effects.

Prospective participants will be informed that it is nonetheless possible you may experience some discomforts during the treatment. These may include temporary decrease in time asleep and accompanying daytime drowsiness. Some people may become anxious while initially following the treatment procedures, with increased worry about their sleep difficulty. Anxiety and worry about sleep difficulty are in fact common among persons with insomnia. Therefore identifying and addressing these possibilities will be directly addressed during the treatment, and participants will be given guidance about what to expect and how to manage should these discomforts occur. Prospective participants will also be informed that persons with certain medical illnesses, certain psychiatric illnesses or other sleep disorders may be at increased potential risk of exacerbation of that illness. This is a possibility for participants with epilepsy, bipolar depression, parasomnia, obstructive sleep apnea or other illnesses which have excessive daytime sleepiness as a feature of the parent disorder. The participant may (or may not) be assigned to a treatment which involves sleep restriction. Sleep loss through sleep restriction may

- 1) Lower the threshold for seizures in persons with epilepsy;
- 2) Precipitate mania in bipolar participants;
- 3) Exacerbate parasomnias;
- 4) Prevent adequate ventilation in patients with obstructive sleep apnea; and/or

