9.7.2 ANALYSIS POPULATIONS

1. **Safety Population:** will include all randomized subjects who meet eligibility criteria and meet with their treatment provider for session 1.

2. **Intent-to-Treat Population:** will include all subjects who meet with their treatment provider for session 1 and for whom the treatment provider determines the subject meets diagnostic criteria for 780.52 Insomnia Disorder.
3. **Pre-Protocol (PP) Population:** will include all subjects who complete the 6 sessions of treatment as well as the 3 month, 6 month and 12 month follow up assessment. It is estimated that 80% of those who complete session 1 will complete session 6. It is estimated that 80% of those who complete session 6 will complete the 3 month, 6 month and 12 month follow up assessments. This will result in 25 participants who will have completed the entire study.

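### The missing-data rules delete participants for incomplete data, a condition the declared intent-to-treat population does not carry, and this may bias the arm comparisons

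*Protocol*

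**What the plan says.** Protocol Section 8.0, Missing Data, first provides for prevention. Forms are reviewed on receipt, and "Subjects who have not completed the data measures and/or specific items will be asked to do so immediately". It then fixes two deletion rules.

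- **Rule A, whole study:** "In any situations in which important missing data cannot be gathered, the subject will be eliminated from the study".
- **Rule B, month 12:** "It is anticipated that in effect 5-10% of subjects will not" complete the 12-month follow-up, and "These subjects will then be eliminated as relates to analyses involving 12 month follow-up data".

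The only further step is a comparison: "Statistical analyses will be conducted to determine whether those with missing data differ significantly from those without missing data". This is a t-test on total ISI at pre-treatment and post-treatment.

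The intent-to-treat population (Synopsis, Section 8.0 and Section 9.7.2) "will include all subjects who meet with their treatment provider for session 1 and for whom the treatment provider determines" that the diagnosis of Insomnia Disorder is met. Complete outcome data are not a condition. Completers of all sessions and all follow-ups form a separate per-protocol set. For that set Section 9.7.2 states: "It is estimated that 80% of those who complete session 1 will complete session 6", and "It is estimated that 80% of those who complete session 6 will complete the 3 month, 6 month and 12 month follow up assessments". It concludes that 25 participants will complete the study.

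**The concern.** These rules are fixed in the protocol, so they are not detail left to a statistical analysis plan. Deleting people because their data are incomplete adds a selection after randomisation. Three places in the protocol give reasons to expect that selection to depend on arm or outcome:

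- Section 7, on the limitations of CBT-I, reports that early loss of sleep and daytime sleepiness lead some patients to drop out. It cites dropout from 0% to 33% across CBT-I trials that used sleep restriction.
- Section 9.3.3 lists lack of efficacy as a reason for discontinuation.
- Section 9.4.10 lets patients whose sleep worsens or is not controlled leave, and requires discontinuation of anyone who starts a new treatment.

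Rule A is the more serious. It removes the person rather than one analysis, so valid earlier data can be lost because of a later gap. It turns on an undefined word, and staff who apply it can know the arm. It can also discard the early-termination assessment that Section 9.3.3 sets out to collect. At stake is whether the comparisons still reflect the groups as randomised.

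**Working it through.** **1. Rules against population.** Intent-to-treat membership needs session 1 and the provider's diagnosis. Rule A adds a third condition, complete important data. Rule B adds a month-12 value, but only for the 12-month hypotheses (8-14). Under Rule B a participant without month 12 stays in the post-treatment hypotheses (1-7) and in the ratings of treatment received (15-16). Section 8.0, Statistics, names a 2 x 4 repeated-measures ANOVA. With two time points this needs both values, so it would impose Rule B's deletion anyway. Rule A is not implied by the method.

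**2. The planned completion figures.** Inputs: 40 per group and 160 in total (Synopsis); 80% and 80% (Section 9.7.2).

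- Per group: 40 x 0.80 x 0.80 = 25.6. This reproduces the stated 25.
- Whole trial: 160 x 0.64 = 102.4. This does not, so 25 is a per-group figure without its label.
- Not completing everything: 160 - 102.4 = 57.6, or 36%.
- Stopping before session 6: 160 - 128 = 32, or 20%.

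**3. The 5-10% figure beside the 80% rates.** Neither a denominator nor a link is given.

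- *Loss per follow-up visit among session-6 completers, visits assumed independent:* the share missing at least one of three is 1 - 0.95^3 = 14.3% to 1 - 0.90^3 = 27.1%. This brackets the 20% implied by the second 80% rate. A per-visit loss of 1 - 0.80^(1/3) = 7.2% gives exactly 20%.
- *Overall month-12 loss of all 160:* 8 to 16 people. If discontinuers are not followed, the 32 early stoppers alone make the loss at least 20%, and the figures cannot both hold. If they are followed, both hold only when (57.6 - 16)/57.6 = 72% to (57.6 - 8)/57.6 = 86% of those who miss something still attend month 12.

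**4. Are discontinuers followed to month 12?** Section 9.3.3 sends them into a 1-week follow-up at Visit 8. Section 9.4.6.3 sends them into the safety follow-up period. The Schedule of Evaluations and Sections 9.1.3 and 9.4.5 place months 3, 6 and 12 under that same heading. The sections do not agree.

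**5. What the ISI comparison can show.** It is described as one comparison of two groups, those with and without missing data, so it is silent on differences between arms. It cannot use a post-treatment ISI that is itself missing. With 8 missing against 152 present, or 16 against 144, and assuming two-sided 5% and 80% power, the detectable difference is about (1.960 + 0.842) x sqrt(1/n1 + 1/n2):

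- 2.802 x sqrt(1/16 + 1/144) = 0.74 SD
- 2.802 x sqrt(1/8 + 1/152) = 1.02 SD

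A non-significant result would therefore say little.

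**6. Why the denominator matters for precision.** Under the same assumptions, unadjusted, the detectable pairwise difference is 2.802 x sqrt(2/n). This gives 0.64 SD at n = 38 and 0.66 at n = 36 (5-10% of 160 lost), against 0.79 at n = 25 if only full completers had month-12 data. Exact t calculations give 0.65, 0.67 and 0.81. These figures do not measure the effect of the deletion rules, because a missing month-12 value stays missing under any rule.

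**The case against.** The best defence is that the rules are narrower than they look. Rule B deletes by analysis and does no more than the stated ANOVA requires. Rule A is limited to important data and comes after forms are checked and re-requested. Early leavers are recalled for a final visit. The ISI comparison shows that some data from people with gaps are kept and used. Assigning hypotheses to populations is commonly left to an analysis plan. No bias has been quantified.

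Much of this stands. A reader might infer that the whole trial is a complete-case analysis, but Rule B does not reach the post-treatment hypotheses. A reader might also infer that the protocol contradicts its own intent-to-treat analysis. No section names such an analysis, so the conflict is with the declared population only.

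The defence does not rescue Rule A. Prevention reduces missing data, but whoever remains incomplete on an undefined criterion is still removed from the study. Comparing those with and without gaps corrects nothing.

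On attrition, a reader might take 25 as an arithmetic error, or the 5-10% as a flat contradiction of the 80% rates. Neither is supported. The first lacks a label, and the second reconciles simply as a per-visit loss among session-6 completers.

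**Conclusion.** The concern holds for the deletion rules, mainly Rule A. Both select on events after randomisation that the protocol itself ties to treatment and outcome. Rule A can also discard data already supplied by members of the declared intent-to-treat population. The arm comparisons may be biased; the document does not allow the direction or size to be stated. The 36% expected not to complete everything shows that the exposed group need not be small, but not all of them would be deleted.

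The intent-to-treat set has its own conditions after randomisation (session 1 and the provider's diagnosis). This point concerns only the further deletion.

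The label on the 25, the denominator of the 5-10% and the follow-up of discontinuers are clarifications, and the weight of the point does not rest on them. The detectable differences rest on an assumed two-sided 5% level and 80% power, and the per-visit reconciliation assumes independent visits.

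**What to change.** 1. **Deletion rules.** Delete Rule A and replace Rule B.
   - Retain all data supplied by intent-to-treat participants.
   - Analyse the repeated continuous outcomes (ISI, Self Report Sleep Measures, Weekly Sleep Log) with a likelihood-based mixed model using all available visits. Put baseline in the response vector, constrained equal across arms. With baseline as a covariate, a participant with no later value would contribute nothing.
   - Take contrasts at post-treatment, at month 12, and on the change between them.
   - State one rule in advance for assigning early-termination assessments to a visit window. This is needed because Section 9.5.3 does not list the ISI at the treatment visits.
   - Add one missing-not-at-random sensitivity analysis.
2. **Attrition wording (minor).** In the Synopsis, Section 8.0 and Section 9.7.2, restate the 25 as about 25 per group, about 102 of 160 in total (64%). State the denominator and meaning of the 5-10%.
3. **Follow-up of discontinuers.** Reconcile Section 9.3.3 with Section 9.4.6.3, the Schedule of Evaluations and Sections 9.1.3 and 9.4.5 on whether they are assessed at months 3, 6 and 12. No rule is proposed here.

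The cost of items 1 and 2 is slightly more analysis work and a few edited sentences, with no extra enrolment. The cost of item 3 depends on the sponsor's decision. If discontinuers are to be assessed, the protocol's own rate implies up to 32 x 3 = 96 further assessments.
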